**Figure 1: Participants selection** 

#### 4.2 Baseline data:

#### **Personal information**:

Total 31.2% (n=24) children were under 2-4 year of age, 23.4% (n=18) were under 5-7 years, 31.2 % (n=24) were also under 8-12 year of age and 14.3% (n=11) children were under 13-18 years of age group. Female to male ratio was 1:1.85. Majority (88.3%) of primary caregiver of studied children were any one of the parents. Most of them belonged to non-local area, other than Karachi territory.

#### Socioeconomic and educational status of Childs care taker:

Total 54.4% (n=42) children's father were labors, 22.1% (n=17) were shopkeepers and 23.4%(n=18) had other occupations. Total 28.6 % (n=22) participate of them were found uneducated, 42.9% (n=33) were educated at School level, while 28.6% (n=22) were educated at higher level. Most of the father's worked on daily Wages, Total 37.7% (n=29) Primary care taker income had less than 10,000 incomes per month and 62.3% (n=48) had more than 10,000 incomes per month.

# **Cancer Information**:

Leukemia (blood cancer) was found to be the commonest cancer among the children (66.2%) and 33.8 % had other cancers. Nearly, 90.0 % caregiver had no history of cancer in their family. While 9.1% (n=7) had an active history of cancer in their family.

#### Pain scale (Visual analog scale):

When asked about the pain felt by the children, majority (n=49) children responded that they were not feeling any pain at that moment. Those who felt pain, was due to the invasive procedure of bone marrow biopsy. Minority complaints about pain were due to abdominal distention and nodules formations.

# Factor associated with Anxiety and depression:

Nearly, 42.9% parents had smoking habits, while 57.1 % did not have smoking habit. The baseline data of parents along with their child are shown in Table 1.

	Total	Intervention	Control	
Section A: Personal information	n=77 (100%)	n=41 (100%)	n=36 (100%)	Chi-Square
				P-Value
1. Child Age:	-	-	-	
2-4years	24(31.2)	13(31.7)	11(30.6)	0.98
5-7years	18(23.4)	10(24.4)	8(22.2)	
8-12 years	24(31.2)	12(29.3)	12(33.3)	
13-18 years	11(14.3)	6(14.6)	5(13.9)	
2. Child Gender:	50/54.0	0 4 ( 5 0 5 )		
Male	50(64.9)	24(58.5)	26(72.2)	0.20
Female	27(35.1)	17(41.5)	10(27.8)	
3. Primary Care Giver:	(0/00.2)	20(02.7)	20(02.2)	0.00
Mother/Father	68(88.3)	38(92.7)	30(83.3)	0.20
Other	9(11.7)	3 (7.3)	6 (16.7)	
4. Residency/Locality:	20(2( 4)	17(41.5)	11(20.6)	0.22
	28(36.4)	1/(41.5)	11(30.6)	0.32
Non-Local	49(63.6)	24(58.5)	25(69.4)	A1 • A
Section B: Socioeconomic and	N=77 (100%)	Intervention	Control	Chi-Square
educational status of Childs care taker		n=41 (100%)	n=36 (100%)	P-Value
5. Occupation	12(54.4)	24(59.5)	19(50)	0.74
	42(54.4)	24(58.5)	18(50)	0.74
Shopkeeper	17(22.1)	8(19.5)	9(25)	
Other	18(23.4)	9(22)	9(25)	
6. Level of education		11(2(0))	11(20.0)	0.00
	22(28.6)	11(20.8)	11(30.6)	0.80
School Education	33(42.9)	1/(41.5) 12(21.7)	16(44.4)	
Higher Education	22(28.6)	13(31.7)	9(25)	
7. Employment status	40((2, ())	29((9.2)	21(59.2)	0.26
Daily wages	49(63.6)	28(08.3)	21(58.5)	0.30
Nonthly Salary	28(36.4)	13(31.7)	15(41.7)	
8. Income per month (Rupees)	20(27.7)	12(20.2)	17(47.2)	0.10
less than 10,000	29(37.7)	12(29.3)	1/(4/.2)	0.10
More than 10,000	48(62.3)	29(70.7)	19(52.8)	
Section C. Concer Information	N = / / (100%)	n=41 (1009/)	Control	D Voluo
0 Diagnosos		II-41 (10070)	II-30 (100 % )	F-value
J. Diagnoses	51(66.2)	28(68.2)	22(62.0)	0.59
Othora	31(00.2) 26(22.8)	20(00.3) 12(21.7)	23(03.9) 12(26.1)	0.58
10 Family History of cancor	20(33.8)	15(51.7)	15(50.1)	
No.	70(00.0)	34(82.0)	33(01.7)	0.25
	70(90.9)	7(17.1)	3(83)	
Section D: Pain scale (Visual analog	N=77 (100%)	Intervention	S(0.5)	Chi Sauara
scale)		n=41 (100%)	n=36(100%)	P_Voluo
11 Pain falt by the child			II-30 (100 /0)	I - Value
No	49(63.6)	23(56.1)	26(72.2)	0.14
Ves	28(36 /)	18(43.0)	10(27.8)	
Section F: Factor associated with	N=77(100%)	Intervention	Control	Chi-Square
Anxiety and depression		n=41 (100%)	n=36(100%)	P-Value
12. Do parent have smoking habits?			1 20(10070)	I - V aiut
No	44(57.1)	21(51.2)	23(63.9)	0.26
Yes	33(42.9)	20(48.8)	13(36.1)	
- •v			1 12(20.1)	1

# Table 1: Socio Demographical Features

#### 4.3 Depression, Anxiety and Stress over study period:

#### 4.3.1 Reliability analysis:

The Cronbach's alpha values of overall DASS measures were 75%, 85.1% and 85.3% at pre, post and 2-week post intervention period respectively. Among the control, their respective values were 79%, 84.9% and 83.5% while from intervention group, these were 69.4%, 81.1% and 78.2% at pre, post and 2-week post intervention respectively. From these values of Cronbach's alpha, it was perceived that consistency among the responses from the participants while responded to the questionnaire showed very good reliability.

# 4.3.2 DASS score and level over pre, post and 2 week post time:

The descriptive statistics of depression, anxiety and stress scores are given in table 2 while distribution of depression, anxiety and stress levels between intervention and control group over study periods are mentioned in table 3.

# **Depression:**

At the baseline depression score was  $15.82 \pm 6.6$ , while 15.6% had no depression and most of the parents 84.4% (n=65) had depression. One week after the depression score was reduced to  $7.97 \pm 5.15$ , in which 62.3% had no depression, while 37.7% (n=29) had depression. The average 'two-week post-depression' score was reduced to  $4.26 \pm 4.36$ , in which 85.7% had no Depression, while 14.3% (n=11) had depression. The percentage of depression in intervention group was reduced from baseline to 22% and 2.4% among intervention group at post and 2-week post intervention while it respectively retained to 55.6% and 27.8% in control group.

## Anxiety:

The average 'pre-anxiety' score was  $11.35 \pm 6.72$ , in which nearly one out of three (n=25) had no anxiety, while 67.5% (n=52) had Anxiety. The average 'post-anxiety' score was  $5.32 \pm 4.5$ , in which about three-quarter (n= 56) had no anxiety, while 27.3% (n=21) had anxiety. The average 'two-week post' anxiety score was  $4.26 \pm 4.36$ , in which 83.1% (n=64) had no anxiety and 16.9% (n=13) had anxiety. The anxiety level reduced to 14.6% to 4.9% in intervention group in post and 2 week post stages respectively though, 41.7% and 30.6% of parents in control group remained anxious in post and 2 week post stages.

#### Stress:

The average 'pre-stress score' was  $16.65 \pm 6.15$ , in which 44.2% (n=34) had no Stress, while 55.8% (n=43) had stress. The average 'post-stress score' was  $8.88 \pm 5.77$ , in which 87% (n= 67) had no stress, while 13% (n=10) had stress. The average 'two-week post stress' score was  $4.73 \pm 4.64$ , in which 96.1% (n=74) had no stress and 3.9% (n=3) had stress. There was steep declined in stress level in intervention group that no parent was in stressed at 2 week after intervention. However, 8.3% of parents in control group still had stress level at final stage of the study.

# Table 2: Average scores of Depression, Anxiety and Stress between intervention and control group

Dependent Variable		Total n=77 (Mean ± SD)	Intervention n=41 (Mean ± SD)	Control n=36 (Mean ± SD)
	Pre-Depression	$15.82 \pm 6.6$	$15.41 \pm 5.97$	$16.28 \pm 7.32$
DEPRESSION	Post-Depression	$7.97 \pm 5.15$	$6.44 \pm 3.94$	$9.72 \pm 5.82$
	Two- Week Post Depression	$4.26 \pm 4.36$	$2.63 \pm 2.98$	$6.11 \pm 4.94$
	Pre-Anxiety	$11.35\pm6.72$	$11.9 \pm 6.51$	$10.72 \pm 7$
ANXIETY	Post-Anxiety	$5.32 \pm 4.5$	$4.2 \pm 3.43$	$6.61 \pm 5.23$
	Two- Week Post Anxiety	$2.98 \pm 3.23$	$1.75 \pm 2.33$	$4.27 \pm 3.61$
	Pre-Stress	$16.65 \pm 6.15$	$16.63 \pm 5.96$	$16.67 \pm 6.45$
STRESS	Post-Stress	$8.88 \pm 5.77$	$7.02 \pm 4.59$	$11 \pm 6.3$
	Two- Week Post Stress	$4.73 \pm 4.64$	$2.88 \pm 3.1$	$6.83 \pm 5.22$

# Table 3:Distribution of depression, anxiety and stress levels between intervention and
control group over study period

Dependent Variable		Yes/No	Total (n=77) n(%)	Intervention (n=41) n(%)	Control (n=36) n(%)
	Pre-Depression	0= No	12(15.6)	6(14.6)	6(16.7)
		1=Yes	65(84.4)	35(85.4)	30(83.3)
DEPRESSION	Post Danrassian	0= No	48(62.3)	32(78)	16(44.4)
DEI RESSION	Post-Depression	1=Yes	29(37.7)	9(22)	20(55.6)
	Two Wook Post Donnession	0= No	66(85.7)	40(97.6)	26(72.2)
	1 wo- week i ost Depression	1=Yes	11(14.3)	1(2.4)	10(27.8)
	Pre-Anxiety	0= No	25(32.5)	11(26.8)	14(38.9)
		1=Yes	52(67.5)	30(73.2)	22(61.1)
ANVIETV	Post-Anxiety	0= No	56(72.7)	35(85.4)	21(58.3)
		1=Yes	21(27.3)	6(14.6)	15(41.7)
	Two- Week Post Anxiety	0= No	64(83.1)	39(95.1)	25(69.4)
		1=Yes	13(16.9)	2(4.9)	11(30.6)
	Pre-Stress	0= No	34(44.2)	19(46.3)	15(41.7)
		1=Yes	43(55.8)	22(53.7)	21(58.3)
STRESS	Post-Stress	0= No	67(87)	40(97.6)	27(75)
SIRESS		1=Yes	10(13)	1(2.4)	9(25)
	Two Wook Post Stress	0= No	74(96.1)	41(100)	33(91.7)
	I WU- WEEK FUST STLESS	1=Yes	3(3.9)	0(0)	3(8.3)

#### 4.3.3 Changes in depression, anxiety and stress scores over different periods:

Table 4 depicted significance values from RM-ANOVA and further post-hoc analyses. Profile plots mentioned as figure 2-4 displayed changes of mean scores of depression, anxiety and stress at baseline, post and 2-week post intervention.

**Depression**: The average depression between intervention and control group was significantly different (P=0.012) over study period (P<0.0001). Post-hoc analysis revealed that a reduction of 7.76 unit decrease in depression score from baseline to post intervention while it significantly reduced to 11.47 unit after 2 weeks of the study.

**Anxiety**: The anxiety level did not show any significant difference between intervention and control group (P=0.172) though both groups displayed concurrently significantly decline in anxiety level at pre, post and 2 week post study period (P<0.0001). Post-hoc analysis also discovered that a reduction of 5.90-unit reduction in Anxiety score from the reference line after intervention and significantly reduced to 8.29 unit after 2 weeks of the study.

**Stress**: The reduction in stress level depicted similar panorama as it was observed in depression score. Post-hoc analysis further exposed a decrease of 7.67-unit reduction in stress score from the baseline line after MBT intervention and significantly reduced to 11.79 units after 2 weeks of the study.

Denendent	Significance value between study groups	Significance value over time	Post Hoc Analysis P-Value with Mean differences		
Variables			Pre & Post	Pre & 2week Post	Post & 2week Post
Depression	0.012	<0.0001	<0.0001 Dif. (7.76)	<0.0001 Dif. (11.47)	<0.0001 Dif. (3.70)
Anxiety	0.172	<0.0001	<0.0001 Dif. (5.90)	<0.0001 Dif. (8.29)	<0.0001 Dif. (2.38)
Stress	0.012	<0.0001	<0.0001 Dif. (7.63)	<0.0001 Dif. (11.79)	<0.0001 Dif. (4.15)

Figure 3: Anxiety scores of intervention and control

Block

-Intervention -Control

 Table 4:
 Significant values of depression, anxiety and stress scores

Figure 4: Stress scores of intervention and control group during study period

	socio demographical features	Pre-Depression Chi-Square P-Value	Pre-Anxiety Chi-Square P-Value	Pre-Stress Chi-Square P-Value
1.	Child Age	0.58	*0.031	0.18
2.	Child Gender	0.42	0.15	0.35
3.	Primary Care Giver	0.69	0.41	0.46
4.	Residency/Locality	0.67	0.58	0.10
5.	Occupation	*0.017	0.25	0.20
6.	Level of education	0.13	0.25	0.15
7.	Employment status	0.28	0.96	0.76
8.	Income per month (Rupees)	0.32	0.07	0.92
9.	Diagnoses	0.97	0.77	0.81
10.	Family History of cancer	*0.02	0.20	0.77
11.	Pain felt by the child	0.12	0.11	0.51
12.	Do parent have smoking habits?	0.92	0.88	0.50
	Significant Association (P-V	/alue <0.05)		

 Table 5 : Association of Socio demographical features with pre-depression, pre-anxiety and pre-stress

The significant association has been identified between child age and pre-anxiety of parents, Occupation and pre-depression of parents and family history of cancer and pre-depression of parents. It is further identified that there is significantly 4 times more likely to have no Anxiety at the time of admission (pre-anxiety), if the child age is < 4 year as compared to the child age > 4 years [OR=4.1, 95%CI(1.0-16.2),P-Value=.042] Moreover, found that there is significantly 20% less likely to have no depression at the time of admission (pre-depression), if Family history has cancer as compared to no history of cancer patient in family [OR=0.20, 95%CI(.047-.880),P-Value=.033]. No association was found with other variable.

Since, almost all variables produced insignificant effect on the outcome variables at three stages of observations. Therefore, these variables were not proceeded for multivariable analysis.

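### Table 5 presents the three smallest of 36 unplanned, unadjusted p-values as significant associations; none survives correction for multiple testing

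*Combined protocol and SAP*

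**What the plan says.** Section 4.3.3 contains Table 5, titled "Association of Socio demographical features with pre-depression, pre-anxiety and pre-stress". It has 12 rows, from child age to parental smoking, and three p-value columns, one for each dichotomised baseline outcome. Three entries are starred as below 0.05: occupation with pre-depression (0.017), family history of cancer with pre-depression (0.02) and child age with pre-anxiety (0.031).

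The text beneath makes four claims:

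1. "The significant association has been identified between child age and pre-anxiety of parents, Occupation and pre-depression of parents", with family history and pre-depression as the third pair.
2. An odds ratio of 4.1 (95% CI 1.0 to 16.2, p = 0.042) for child age, called significant.
3. An odds ratio of 0.20 (0.047 to 0.880, p = 0.033) for family history, also called significant.
4. "No association was found with other variable".

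For categorical variables, section 3.14 describes only frequencies and percentages. It mentions no association tests, no exact tests and no adjustment for multiplicity.

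**The concern.** Thirty-six tests at an unadjusted 0.05 will usually produce some small p-values even if no characteristic is related to any outcome. Stating the three smallest as findings, with no word on how many tests were run or that they were unplanned, invites a reader to take occupation, family history and child age as identified correlates of parental distress. The closing sentence invites the opposite error, that the other characteristics have been shown not to matter.

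A secondary concern is that two of the three starred results are in the pre-depression column, where the split is very uneven: section 4.3.2 reports that "15.6% had no depression and most of the parents 84.4% (n=65) had depression". Some expected cell counts there are too small to rely on the chi-square approximation.

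**Working it through.** **Inputs.** The 36 p-values are from Table 5. Baseline splits (No/Yes, Table 3) are depression 12/65, anxiety 25/52 and stress 34/43, out of 77. Occupation is 42/17/18 (section 4.2). Family history is 7 in the section 4.2 text but 7 + 3 = 10 in the Table 1 arm columns.

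**Reproducing a printed result.** With 12 non-depressed parents and 7 to 10 family-history cases, only one 2×2 table gives the printed figures: 4 of 10 non-depressed with family history and 8 of 67 without.
- Pearson p = 0.0225 (printed 0.02).
- Odds ratio for having depression = (6 × 8)/(4 × 59) = 0.203.
- SE of the log odds ratio = √(1/4 + 1/6 + 1/8 + 1/59) = 0.747; 95% CI 0.047 to 0.880; p = 0.033. All as printed.

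So the printed chi-square value is a plain, uncorrected Pearson p. This table has more non-depressed parents among those with a family history (40% against 12%), the reverse of the sentence in the text. An odds ratio of 0.20 is also 80% lower odds, not 20%.

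**Chance expectation.** 36 × 0.05 = 1.8; this needs no independence. If the tests were independent, P(at least one) = 1 − 0.95^36 = 0.84 and P(three or more) = 0.27.

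**Correction over 36 tests** (the fourth-smallest p is 0.07):

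| Raw p | Holm | Benjamini-Hochberg q |
|---|---|---|
| 0.017 | 36 × 0.017 = 0.61 | 0.36 (from the next row) |
| 0.02 | 35 × 0.02 = 0.70 | (36/2) × 0.02 = 0.36 |
| 0.031 | 34 × 0.031 > 1, so 1.00 | (36/3) × 0.031 = 0.37 |

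**Smaller families.** Within the 12 depression tests, the smallest Holm p is 12 × 0.017 = 0.20 and the smallest q is (12/2) × 0.02 = 0.12. With a family of only three outcomes per characteristic, Bonferroni gives 3 × 0.017 = 0.051, 3 × 0.02 = 0.060 and 3 × 0.031 = 0.093. None is below 0.05.

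**Sparse cells.** Expected count = row total × column total / 77.
- Occupation, no depression: 42 × 12/77 = 6.55; 17 × 12/77 = 2.65; 18 × 12/77 = 2.81.
- Family history, no depression: 10 × 12/77 = 1.56, or 7 × 12/77 = 1.09.
- Child age with anxiety, smallest cell: 11 × 25/77 = 3.57.

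Exact tests: family history, Fisher p = 0.044 (Yates 0.070). For occupation, the two tables that fit the printed 0.017 give exact p = 0.016 and 0.018.

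**Power** (assumed odds ratio, characteristic split 50:50, Pearson test at 0.05, simulated, so approximate):

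| Assumed OR | Depression | Anxiety | Stress |
|---|---|---|---|
| 3 | 38% | 62% | 64% |
| 4 | 54% | 80% | 83% |

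Of the 33 non-significant tests, 10 are in the depression column and 23 in the other two.

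**The case against.** The strongest reply is that little hangs on Table 5. All 36 p-values are printed, so a reader can count the tests. The associations are outside the stated objective, do not appear in the abstract's results, the conclusion or the recommendation, and do not touch the comparison between arms. Whether baseline associations of this kind need a correction across 36 tests is partly a matter of convention. This stands as an argument about severity. It does not rescue the wording, because the text calls the three results significant without qualification and they fail under every family considered.

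Some stronger readings are tempting but not supported:

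- *The sparse cells invalidate the starred results.* They do not. Exact tests leave occupation (about 0.017) and family history (0.044) below 0.05 before correction. Only the conservative Yates version moves family history above it, and the age result has no expected count below 3.57. Multiplicity is the deciding point.
- *All the non-significant results are uninformative.* The 38% figure applies only to depression. Power in the other columns is better, though still modest at an odds ratio of 3. The closing sentence can also be read as a literal report of what was found.
- *Table 5 is why multivariable analysis was dropped.* The document gives as its reason a lack of effect across all three assessment times, whereas Table 5 covers baseline only. Correction would leave fewer significant variables, so it would not itself change that decision.

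The 0.84 and 0.27 are approximate. The three outcomes come from the same parents and are probably correlated.

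**Conclusion.** The point holds on multiplicity. Three unplanned results are stated as significant although about 1.8 would be expected by chance, and none remains after correction, whether over 36 tests, 12 tests or three. This does not show that the three associations are false, only that these data do not establish them. Equally, the other 33 results do not establish absence.

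The conclusion rests on the printed p-values being unadjusted. That is inferred from the 0.05 threshold, the silence of section 3.14 and the reproduction of one value as a plain Pearson p. The power figures rest on assumed odds ratios and an even split. The family-history count depends on whether 7 or 10 is right, which the documents leave unresolved; the printed odds ratio fits 10.

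Severity is minor: the treatment comparison and the trial's conclusions are not affected.

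**What to change.** - Label Table 5 exploratory and state that it contains 36 tests not described in section 3.14.
- Analyse the continuous baseline DASS-21 scores against each characteristic. Use Fisher's exact test for any sparse table kept categorical.
- Print Benjamini-Hochberg q-values over all 36 tests beside the raw p-values.
- Reconcile the family-history total (7 in the section 4.2 text, 10 from the Table 1 arm columns).
- Revise all four claims beneath the table: the sentence naming the associations, both odds-ratio sentences and the closing sentence on other variables. They should say that, on the printed p-values, no association remained after correction for 36 tests and that moderate associations cannot be ruled out. Update this if the re-analysis differs. If the family-history odds ratio is kept as a description, its direction and size must agree with the underlying table.

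The cost is re-running one table on data already in hand and rewriting four sentences. The downside is the loss of three claimed associations.

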#### 3.13 Study Variables

# 3.13.1 Dependent Variable:

Depression (D) anxiety (A) and stress (S) were outcome variables. [63]. They were identified by using DASS-21 Scale. The use of DASS-21 scale was evident in different research studies from Pakistan [62, 64-67]. There were 21 questions in this scale equally divided into three parts having seven questions for Depression, Anxiety and stress respectively. Each question had four level of measurement 0, 1, 2 and 3, represent past week experiences. 0 means not applicable to person, 1 means applicable to some degree or sometime, 2 means applicable to considerable degree or good part of time, 3 means applicable to person very much or most of the time. Each question was separated for Stress(s), Anxiety (a) and Depression (d). The questions focusing the concept (1) (s) hard to wind down, (2)(a) dryness of mouth, (3)(d) experience of positive feeling, (4)(a) breathing difficulty, (5)(d) difficulty in initiation of work, (6)(s) overreaction according to situation, (7)(a) experience of trembling in hand, (8)(s) use of excessive nervous energy, (9)(a) worriedness about panic situation, (10)(d)noting to look forward, (11)(s) getting agitated, (12)(s) difficulty in relaxation, (13)(d)feeling of downhearted and blue, (14)(s) lack of tolerance, (15)(a) feeling of panic, (16)(d)lack of enthusiasm, (17)(d)lack of worthiness as a person, (18)(s) feeling of somewhat sensitive, (19)(a) palpitation and increase of heart beat, (20)(a) feeling of scary and (21)(d) feeling of meaningless life. The cut-off scoring for (1) Depression was Normal (0-9), Mild (10-13), Moderate (14-20), severe (21-27) and extreme Severe (28+), (2) Anxiety was Normal (0-7), Mild (8-9), Moderate (10-14), severe (15-19) and extreme Severe (20+)and (3) Stress was Normal (0-14), Mild (15-18), Moderate (19-25), severe (26-33) and extreme Severe (34+). For further categorical analysis, the depression, anxiety and stress were dichotomized into "No" and "Yes" where "Yes" category was generated while combining the statuses of "mild", "moderate", "severe" and "extremely severe". The Scores on DASS-21 scale was multiplied by 2 to get the final score.

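### Section 4.3.3 reports the family-history odds ratio in the wrong direction and misreads its size: the figures correspond to less baseline depression, not more

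*Combined protocol and SAP*

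**What the plan says.** Table 5 crosses 12 socio-demographic features with baseline depression, anxiety and stress and flags three associations as significant. One is family history of cancer with baseline depression, chi-square p = 0.02.

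The text under the table describes it as "significantly 20% less likely to have no depression at the time of admission", "if Family history has cancer as compared to no history of cancer patient in family", with "OR=0.20, 95%CI(.047-.880),P-Value=.033".

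On how many parents had a family history, section 4.2 (Cancer Information) states "While 9.1% (n=7) had an active history of cancer in their family". The arm columns of Table 1 give 7 of 41 in the intervention group and 3 of 36 in the control group.

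Section 3.13.1 codes depression as present for any category from mild upwards and absent for the normal range. Table 3 gives 12 parents without and 65 with depression at baseline.

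**The concern.** The sentence raises three questions.

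- **Size.** An odds ratio of 0.20 means odds lower by 80%. The sentence reads the ratio itself as the percentage reduction.
- **Direction.** Being less likely to have no depression means being more likely to have depression. Only 12 of 77 parents were not depressed and few had a family history, so a significant odds ratio as low as 0.20 for no depression looks hard to obtain.
- **Denominator.** The number with a family history is 7 in one place and 10 in another.

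This is one of three associations reported as significant and one of only two given an effect estimate. A reader who takes the sentence at its word would treat family history as a risk marker for depression at the start of chemotherapy.

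**Working it through.** **Inputs**

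- Baseline depression: 12 no, 65 yes, N = 77 (Table 3).
- Family history, arm columns of Table 1: yes 7 + 3 = 10; no 34 + 33 = 67.
- Family history, section 4.2: yes 7, hence no 70.
- Reported: OR 0.20, 95% CI 0.047 to 0.880, p = 0.033 (section 4.3.3); chi-square p = 0.02 (Table 5).

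**Method.** With both margins fixed, one cell determines the table. Let k be the number of parents with a family history who were not depressed. For each k, compute the odds ratio, SE(log OR) = √(1/a + 1/b + 1/c + 1/d), the Wald interval exp(log OR ± 1.96 × SE) and the two-sided Wald p.

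**Family history = 10**

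| k of 10 not depressed | OR for no depression | OR for depression (95% CI) | Wald p |
|---|---|---|---|
| 0 | 0 | not estimable | – |
| 1 | 0.57 | 1.77 (0.203 to 15.4) | 0.61 |
| 2 | 1.43 | 0.70 (0.130 to 3.80) | 0.68 |
| 3 | 2.76 | 0.36 (0.079 to 1.66) | 0.19 |
| **4** | **4.92** | **0.203 (0.0470 to 0.8801)** | **0.033** |
| 5 | 8.57 | 0.117 (0.027 to 0.505) | 0.004 |

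Beyond k = 5 the odds ratio for depression keeps falling.

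**Reproducing the reported figure (k = 4).** With a family history, 6 depressed and 4 not; without, 59 depressed and 8 not.

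- OR for depression = (6/4) / (59/8) = 1.5 / 7.375 = 0.2034.
- SE = √(1/6 + 1/4 + 1/59 + 1/8) = √0.5586 = 0.7474.
- log OR = −1.5926; 95% CI = exp(−1.5926 ± 1.4649) = 0.0470 to 0.8801.
- z = 1.5926 / 0.7474 = 2.13; p = 0.0331.
- Uncorrected chi-square = 77 × (6×8 − 4×59)² / (10 × 67 × 65 × 12) = 2,721,488 / 522,600 = 5.21; p = 0.0225.

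The odds ratio, both limits, the p-value in the text and the p-value in Table 5 all match.

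**The direction as worded.** For an odds ratio of no depression below 1, these margins allow only 0 (k = 0) or 0.57 (k = 1; CI 0.065 to 4.93). A value of 0.20 cannot occur.

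**Family history = 7.** The nearest table has k = 3: OR for depression 0.197 (0.038 to 1.03), p = 0.054. It misses the reported interval and p. Its neighbours give 0.417 (k = 2) and 0.097 (k = 4). An odds ratio of no depression below 1 could only be 0 or 0.89. The worded direction therefore fails on this total too.

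**Wider search.** Across all 2×2 tables with N from 74 to 77, the reported odds ratio and interval arise only from the cells 4, 6, 8 and 59, at N = 77. On the printed margins these fit in one way.

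**Which family-history total was analysed.** Comparing 7/41 with 3/36, the uncorrected chi-square p is 0.255; Table 1 prints 0.25. The arm counts thus reproduce both Table 1's p-value and the odds ratio.

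**What the table says.** Depressed: 6/10 = 60.0% with a family history, 59/67 = 88.1% without. Not depressed: 40.0% against 11.9%. The odds ratio for no depression is 1/0.2034 = 4.92 (1.14 to 21.3). On the risk scale, 0.600/0.881 = 0.68, a 32% lower risk of depression.

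**Strength of evidence.** The smallest expected count is 10 × 12/77 = 1.6. Fisher's exact p is 0.044 and the continuity-corrected chi-square p is 0.070. Table 5 holds 12 × 3 = 36 tests, of which 36 × 0.05 = 1.8 would fall below 0.05 by chance if none of the associations were real.

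**The case against.** The strongest reply is that the family-history by depression table is nowhere printed. The counts 6/10 and 59/67 are reconstructed, and they assume that the yes and no labels in Tables 1 and 3 are right in a document already inconsistent on family history. That stands as a reason to confirm the counts from the data. It does not rescue the sentence, since the worded direction is impossible under either family-history total and the misreading of 0.20 as 20% needs no reconstruction.

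Second, it cannot be told which label slipped. The same 0.20 is also the odds ratio of no depression for parents without a family history against those with one. True, but that is the same table and the same association, and it contradicts the stated comparison just as much.

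Third, the family-history rows in the total column of Table 1 are poorly legible in the available text, so the clean source for 7 (9.1%) is section 4.2. The conflict between that figure and the arm columns remains.

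Fourth, this is a fragile baseline side result. The Discussion and conclusions do not use it, and section 4.3.3 takes none of these variables into a multivariable model. This is correct and limits the importance of the error, but the reported result is still wrong.

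**Conclusion.** The concern holds. The reported odds ratio, interval and p-value are correct for depression, family history versus none, but the text attaches them to no depression and reads 0.20 as a 20% reduction. Family history went with about 80% lower odds of baseline depression (60% against 88% depressed), equivalently 4.92 times the odds of no depression (1.14 to 21.3). The family-history total of 7 in section 4.2 conflicts with 10 from the arms, and 10 is the count that reproduces the analysis.

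This rests on the printed margins and labels being right; given them, the match is unique. The correction should be made, but the association is exploratory, rests on 10 parents with a family history, and has no bearing on the comparison of intervention with control.

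**What to change.** 1. Cross-tabulate family history by baseline depression from the data file, confirm the counts, and settle whether 7 or 10 parents had a family history.
2. If the counts are confirmed, replace the sentence in section 4.3.3 with, for example: *Parents with a family history of cancer had lower odds of baseline depression (6/10 vs 59/67 depressed; OR 0.20, Wald 95% CI 0.047 to 0.880; Fisher exact p = 0.044). This is exploratory, one of 36 unadjusted tests.* Fisher's test is suggested because the smallest expected count is 1.6. If the Wald p of 0.033 is kept, name the test.
3. Correct the family-history total to 10 (13.0%) against 67 (87.0%) in section 4.2 and in the total column of Table 1.

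The cost is one cross-tabulation, one Fisher test, and edits to one sentence in section 4.3.3 and one total in section 4.2 and Table 1. No new data are needed and no treatment analysis is rerun.
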